Study Protocol and Statistical Analysis Plan

1. Data Source

This study utilized data from Taiwan's National Health Insurance (NHI) program, a universal health system established in 1996 that covers over 99% of the population. The claims database provides comprehensive and validated medical records for research use. All personal identifiers were encrypted to protect patient privacy. The study protocol was approved by the Institutional Review Board and conducted in accordance with the Declaration of Helsinki.

2. Study Design

A **nested retrospective cohort design** was adopted to evaluate the association between influenza vaccination (IV) and clinical outcomes following fracture-related hospitalizations.

From the nationwide NHI cohort of more than 23 million insured individuals, we identified **561,566 patients aged ≥65 years** admitted for fracture treatment between 2009 and 2020. Among them, **213,381** received IV within 12 months prior to admission, while **348,185** had not.

To reduce confounding, **1:1 propensity score matching (PSM)** was performed between vaccinated and nonvaccinated patients. Matching variables included:

- Demographics: age, sex
- Socioeconomic status (low-income vs. non-low-income)
- Fracture type and comorbidities (within 24 months)
- Emergency visits and hospitalizations during the prior year

3. Outcomes

The **primary outcomes**, assessed within 30 days postadmission, included:

- Pneumonia
- Septicemia
- Urinary tract infection
- Intensive care use
- Hospital length of stay
- Total medical expenditure
- 30-day mortality

Postfracture infections were identified by physician-coded diagnoses during hospitalization or subsequent claims. Patients with pneumonia or septicemia within 6 months before the fracture were excluded.

4. Measures and Definitions

- **Socioeconomic status:** categorized as low-income or non-low-income per NHI copayment exemption criteria.

- **Comorbidities:** identified from 24-month pre-fracture claims using *ICD-9-CM* codes.
- **Postfracture infections:** defined by ICD-9-CM diagnostic codes (listed in Table S1).
- **Influenza vaccine types:** summarized in Table S2.

5. Statistical Analysis

Propensity scores were estimated using **multivariable logistic regression**, including clinically relevant covariates (Table 1). Matching was performed via a **greedy algorithm** with a caliper width of 0.2 SD of the logit of the propensity score.

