- **Categorical variables:** summarized as counts and percentages; compared using the *chi-square test*.
- **Continuous variables:** expressed as mean \pm SD; compared using *independent t-tests*.
- **Risk estimation:** Adjusted odds ratios (ORs) with 95% confidence intervals (CIs) were derived from logistic regression to assess IV effects on infections and mortality.
- **Sensitivity analyses:** stratified by age, sex, comorbidity burden, and fracture type.

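### Socioeconomic status is matched only as exempt low-income versus everyone else, so residual socioeconomic confounding is possible, of unknown direction, and not assessed.

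*Combined protocol and SAP*

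**What the plan says.** Section 4 (Measures and Definitions) states that socioeconomic status is "categorized as low-income or non-low-income per NHI copayment exemption criteria". The matching list in section 2 (Study Design) carries the same two-level variable. The rest of that list covers demographics, type of fracture, comorbid conditions and recent acute care use ("Emergency visits and hospitalizations during the prior year"). It has no insured amount, premium band, occupation or area variable.

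Section 5 (Statistical Analysis) refers to a Table 1 for the propensity covariates, which is not in the public text. The odds ratios "were derived from logistic regression to assess IV effects on infections and mortality", but the adjustment set is not listed. The sensitivity analyses are "stratified by age, sex, comorbidity burden, and fracture type". None of them concerns socioeconomic status or unmeasured confounding.

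**The concern.** Under the binary definition every patient above the exemption line has the same value. A near-poor and a wealthy patient are interchangeable in the match, except to the extent that correlated covariates separate them. A balance table for the binary could look perfect while income within the non-exempt group stayed imbalanced.

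Income is plausibly linked to vaccine uptake and to some outcomes; intensive care use and expenditure are the obvious candidates. If those links exist after the other matching variables are taken into account, the estimates carry a bias that nothing in the plan would reveal. In a cohort this large, chance error is small, so even a modest systematic bias can decide whether an interval excludes 1.

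**Working it through.** **Figures in the documents.** Section 2 gives "213,381 received IV within 12 months prior to admission, while 348,185 had not". The groups add up to the stated cohort: 213,381 + 348,185 = 561,566. The vaccinated share is 213,381 / 561,566 = 38.0%, and 1:1 matching can give at most 213,381 pairs. The documents give no exempt share, no income association and no outcome risk. Everything below that needs one of these is an assumption.

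**Step 1: how much income variation a binary captures.** Treat income as a standard normal scale cut at its lower p-th quantile z. The share of variance captured is φ(z)² / [p(1 - p)].

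- p = 1%: 0.0267² / 0.0099 = 7%
- p = 5%: 0.1031² / 0.0475 = 22%
- p = 10%: 0.1755² / 0.09 = 34%
- p = 20%: 0.2800² / 0.16 = 49%
- p = 30%: 0.3477² / 0.21 = 58%

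So more than half is left uncaptured only if the exempt share is below about 20%.

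**Step 2: what that could do to an odds ratio.** Let X be standard normal income, with logit P(vaccinated) = a + bX and logit P(outcome) = c + gX. Choose a to give 38.0% vaccinated and c to give an assumed 3% outcome risk. Vaccination has no effect. Within each level s of the matched variable, take the risk in the vaccinated (r1s) and in the nonvaccinated (r0s), and weight both by the vaccinated distribution ws. Then R1 = Σ ws·r1s, R0 = Σ ws·r0s, and the apparent odds ratio is [R1/(1 - R1)] / [R0/(1 - R0)]. The slopes are to be read as conditional on the other matching variables, which the model leaves out. Numerical integration gives:

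| Slopes b / g | Unmatched | Binary, 1% exempt | Binary, 5% | Binary, 10% | Five error-free bands |
|---|---|---|---|---|---|
| 0.1 / -0.1 | 0.990 | 0.991 | 0.992 | 0.994 | 0.999 |
| 0.2 / -0.2 | 0.961 | 0.964 | 0.970 | 0.975 | 0.996 |
| 0.3 / -0.2 | 0.943 | 0.947 | 0.956 | 0.963 | 0.994 |

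The share of the log-odds-ratio bias removed is 1 - ln(OR matched) / ln(OR unmatched). For 0.2 / -0.2, with unrounded values, the binary removes about 8% (1% exempt), 24% (5%) and 36% (10%); error-free bands remove about 90%. The other two rows give nearly the same shares.

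**Step 3: size against precision.** At 3% risk and 213,381 pairs, SE(log OR) ≈ √[2 / (213,381 × 0.03 × 0.97)] = √(2 / 6,209) = 0.018. An estimate below exp(-1.96 × 0.018) = 0.965 would exclude 1. The residual bias runs from |ln 0.994| / 0.018 = 0.3 SE to |ln 0.947| / 0.018 = 3.0 SE. For 0.2 / -0.2 it is 2.0 SE at 1% exempt and 1.4 SE at 10%. Fewer pairs would raise the SE and lower these ratios.

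**Step 4: direction.** With a 5% outcome risk, odds ratios per SD of income of 0.8 for vaccination and 0.70 for the outcome, and 1% to 10% exempt, a null effect appears as 1.072 to 1.045. If income is unrelated to vaccination or to the outcome, the result is 1.000.

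**Step 5: an imperfect income measure.** For 0.2 / -0.2, fifths of a proxy correlated 0.5 with income give 0.970, and 0.978 at correlation 0.7, against 0.996 without error. The 0.970 is no better than the binary alone at 5% exempt.

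**The case against.** A reader might infer that the binary leaves most income variation unmatched as a matter of fact, and that every outcome is therefore confounded with income in favour of vaccination. The documents support neither. The first part needs an exempt share that is not given. The second needs income, given the other matching variables, to be related both to vaccination and to each outcome. No such association is shown for any of the seven outcomes, and step 4 shows that the bias can vanish or reverse. Length of stay and expenditure are not covered by the calculation at all.

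Four further points stand. Matching on comorbidity and prior acute care may absorb part of any income gradient. The matching list is not worded as exhaustive, and Table 1 may hold more covariates. The plan says that matching is meant to reduce confounding; it does not claim to have controlled income. And the documents describe a claims database without mentioning income bands or dependant status, so the availability of a finer measure is an assumption.

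These points limit how strongly the concern can be put. They do not remove it. Section 4 gives the plan's own definition of socioeconomic status, that definition is binary, and no planned analysis examines what it leaves out.

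**Conclusion.** The concern holds in limited form. The single listed socioeconomic variable cannot balance income among non-exempt patients except through correlated covariates, and the remainder is not assessed. Under the stated assumptions a null effect would appear as about 0.947 to 0.994, which is from negligible to about three standard errors at the maximum number of pairs. These figures illustrate what could happen; they do not estimate the bias in this study. They rest on the assumed slopes, exempt share, outcome risk and normal income scale. What depends least on the slopes is the relative comparison: for exempt shares of 1% to 10%, the binary removes roughly a third or less of whatever income bias exists, and accurate bands would remove most of it.

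**What to change.** In sections 2 and 4, keep exempt low-income as the lowest category. If the NHI enrolment data hold them, add ordered income or premium bands above it, together with insured-versus-dependent status, and put these in the propensity score. Report the exempt share, check balance by band, and show the results beside those of the binary-only match.

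If no finer measure is available, add a quantitative bias analysis for residual socioeconomic confounding (an E-value is one option), and describe socioeconomic status as only partly controlled. In either case, list the full set of propensity covariates.

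The cost is one more variable or so from the enrolment data and a re-run of the match. For dependants the band reflects the insured relative's income, so the gain may fall well short of the error-free figure, as step 5 shows. Because the exempt group stays as its own category, the banded version should not control income less well than the present binary.

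### Comorbidities and infection outcomes are defined in ICD-9-CM alone for admissions up to 2020, and nothing in the plan would absorb a change of code system

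*Combined protocol and SAP*

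**What the plan says.** - Section 2 (Study Design) describes patients "admitted for fracture treatment between 2009 and 2020", a cohort of "561,566 patients aged ≥65 years".
- Section 4 (Measures and Definitions) has comorbidities "identified from 24-month pre-fracture claims using *ICD-9-CM* codes" and postfracture infections "defined by ICD-9-CM diagnostic codes (listed in Table S1". Table S1 is not in the text available for review.
- Section 3 (Outcomes) adds: "Postfracture infections were identified by physician-coded diagnoses during hospitalization or subsequent claims". It names no code version. Pneumonia, septicemia and urinary tract infection are three of the seven primary outcomes.
- Section 3 also states the prior-infection exclusion: "Patients with pneumonia or septicemia within 6 months before the fracture were excluded". No code system is given for it, and none is given for the fracture itself.
- The matching variables in section 2 cover demographics, income status, fracture type, comorbidities and recent use of care. Calendar year is not among them. Section 5 refers the propensity-score covariates to Table 1, which is also not in the text.
- The sensitivity analyses in section 5 are by age, sex, burden of comorbidity and type of fracture. None is by calendar period.

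**The concern.** With the 24-month look-back, the study draws on claims from about 2007 to 2020. One named code version is applied to all of them, as a stated rule rather than by omission. If the claims moved to ICD-10-CM within that span, a search restricted to ICD-9-CM finds nothing in the later records and returns a zero that looks like a true negative.

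Two things would follow. The three infection outcomes would be zero by construction for later admissions, so their recorded incidence would be too low. Comorbidities, which drive the matching, would be under-recorded for those patients and in time not recorded at all. Matching would then rest on age, sex, income status, fracture type and prior use of care. The second effect reaches all seven primary outcomes, including mortality, because it weakens confounding control whatever the outcome.

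**Working it through.** **Inputs from the documents.** 12 admission years (2009 to 2020); 561,566 patients, 213,381 vaccinated and 348,185 not; a 24-month comorbidity look-back; a 6-month exclusion window.

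**Check of the plan's own figure.** 213,381 + 348,185 = 561,566, which agrees exactly (38.0% vaccinated).

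**Assumptions, not in the documents.** (a) The claims changed to ICD-10-CM on 1 January of year Y. (b) Admissions are spread evenly over the 12 years. (c) ICD-9-CM codes capture nothing after the change. (d) For the odds-ratio illustration only, the true infection risk in the nonvaccinated is 5%.

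**Step 1: share of admissions affected.** Infection outcomes are lost for admissions after the change: (2021 − Y)/12. The comorbidity look-back is fully blank from two years later: (2021 − Y − 2)/12.

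| Change at start of | Infection outcomes lost | Look-back fully blank |
|---|---|---|
| 2015 | 6/12 = 50% | 4/12 = 33% |
| 2016 | 5/12 = 42% | 3/12 = 25% |
| 2017 | 4/12 = 33% | 2/12 = 17% |
| none by end of 2020 | 0 | 0 |

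For 2016, on prematching counts, 561,566 × 5/12 is about 234,000 patients and 561,566 × 3/12 about 140,000. Over a wider span of dates, the share losing the infection outcomes runs from 75% (2012) to 8% (2020).

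**Step 2: recorded infection risk.** With a 2016 change, 0.05 × (1 − 5/12) = 0.0292. A true 5% is recorded as 2.9%.

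**Step 3: odds ratio with the same calendar mix in both arms.** With a true odds ratio of 1.00, both arms shrink alike and 1.00 is observed. With a true 0.80, the vaccinated odds are 0.8 × 0.05/0.95 = 0.0421, so the risk is 0.0404. The recorded risk is 0.0404 × 7/12 = 0.0236, with odds 0.0241. The control odds are 0.0292/0.9708 = 0.0300. The ratio, from unrounded values, is 0.803. Loss alone barely moves it.

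**Step 4: odds ratio with a 5-point difference in calendar mix.** 2016 change, true odds ratio 1.00:
- 5 points more post-change admissions among the vaccinated: recorded risk 0.05 × (0.5833 − 0.05) = 0.0267, odds 0.0274, ratio to 0.0300 about 0.91.
- 5 points fewer: 0.05 × (0.5833 + 0.05) = 0.0317, odds 0.0327, ratio about 1.09.

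The same calculation for a 2015 change gives 0.90 and 1.10. Over changes from 2012 to 2020, the null range narrows from 0.80–1.20 to 0.94–1.06.

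**The case against.** The strongest objection is that the event creating the problem is not in the documents. Nothing in them says the claims ever changed code system, so the period 2009 to 2020 and a definition in ICD-9-CM do not contradict each other on the page, and the effect may be nil. In addition, Table S1 cannot be seen and may list ICD-10-CM codes under a loose label. The plan also reports a cohort running to 2020; if a change occurred, later fractures were evidently found by other codes, which points to incomplete wording rather than a failed analysis. This stands as a limit on the claim: the loss is conditional. It does not remove the point, because section 4 states a single-system rule, and the plan contains nothing that would reveal or absorb a change.

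A reader might infer several stronger things that the documents do not support:
- That later patients escape the pneumonia and septicemia exclusion. Section 3 names no code system for it, so this follows only if it uses the same list.
- That every patient admitted after a change shows no comorbidity. Those admitted in the first 24 months keep part of the look-back in the old codes.
- That late patients with hidden comorbidity are paired with early patients who truly have none. Matching is on a propensity score, so two late patients can equally be paired.
- That the infection odds ratios must be biased. With equal calendar mix they are nearly unchanged, and the documents give no evidence of imbalance. Nor do they show it is prevented: section 2 does not list calendar year, though Table 1 might.
- That all seven primary outcomes go missing. Intensive care use, length of stay, expenditure and mortality are not defined by these codes; they are touched only through the matching.

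**Conclusion.** The point holds conditionally. As written, section 4 applies ICD-9-CM alone to comorbidities and infections for admissions through 2020, with no mapped codes, no listed matching on calendar year and no coding-era check. If the claims moved to ICD-10-CM in that period, three primary outcomes are zero by construction after the change. The comorbidity look-back is partly blank for 24 months and fully blank from then on. For a change at the start of 2015 to 2017 and even admissions, that is 50% to 33% of admission years for the outcomes and 33% to 17% for a fully blank look-back.

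The certain consequences of such a change are understated infection risks and weaker comorbidity matching. Bias in the infection odds ratios depends mainly on a difference in calendar mix between the arms: about 0.91 or 1.09 in place of 1.00 for a 5-point difference, at an assumed 5% risk and a 2016 change. If no change took place, none of this applies. Whichever is true, the plan should say so, because until it does the infection definitions cannot be reproduced for the full period.

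**What to change.** 1. In section 4 and Table S1, state which code system applied to the claims in each year, look-back years included. Define comorbidities, infection outcomes, the prior-infection exclusion and the fractures by ICD-9-CM codes before any change and mapped ICD-10-CM codes after it. Accept either system in look-backs that straddle the change.
2. Tabulate the prevalence of each item by calendar quarter, to detect a step at the change.
3. Add calendar year of admission to the propensity score and to the matching variables in section 2. This evens out the calendar mix between the arms; it does not recover events that the codes miss, so it does not replace item 1.
4. Add a sensitivity analysis limited to admissions before the change.
5. If only ICD-9-CM codes were used across a change, restrict the admission period to the ICD-9-CM years and restate the counts.

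If both systems were already used, item 1 amounts to a corrected sentence and a code table. If there was no change, a sentence saying so removes the need for the mapping and the pre-change analysis. Otherwise the cost is a code map and a rerun of cohort selection and matching on data already held. The downside is that some mappings are not one-to-one and the cohort counts may change.

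### The analysis takes no account of treating hospital; if vaccine uptake differs between hospitals, the 95% CIs are too narrow and the tests reject too often

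*Combined protocol and SAP*

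**What the plan says.** Section 2 (Study Design) draws the sample "From the nationwide NHI cohort of more than 23 million insured individuals" and studies "clinical outcomes following fracture-related hospitalizations". It reports "561,566 patients aged ≥65 years", of whom 213,381 were vaccinated and 348,185 were not. Exposure is defined per patient and before admission: the vaccinated are those who "received IV within 12 months prior to admission". The matching variables listed there are age, sex, income status, fracture type, comorbidities and prior use of care. Hospital and region are not among them.

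Section 3 (Outcomes) lists three infections, intensive care use, length of stay, expenditure and 30-day mortality as primary.

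Section 5 (Statistical Analysis) gives the inferential methods. For infections and mortality: "Adjusted odds ratios (ORs) with 95% confidence intervals (CIs) were derived from logistic regression to assess IV effects on infections and mortality". Categorical variables are compared by chi-square test and continuous variables by independent t-test. No other method is named for intensive care use, length of stay or expenditure. Section 5 mentions no random effect, GEE, hospital stratum or cluster-robust variance. The documents do not say how many hospitals there are, how far outcomes or uptake vary between them, or whether the claims identify the hospital.

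**The concern.** Intensive care use, length of stay, cost and diagnostic coding plausibly depend on where a patient is treated. In a nationwide inpatient cohort each hospital contributes many patients, whose outcomes are then correlated. The named methods count each patient as an independent unit. If the vaccinated share also differs between hospitals, part of the hospital-to-hospital variation in outcome enters the vaccinated-versus-unvaccinated contrast, and the model standard error omits it. With several hundred thousand patients the nominal standard error is very small, so even modest hospital variation can be large beside it. At stake are the coverage of the 95% intervals and the false-positive rate of the tests.

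**Working it through.** **The plan's own figure.** 213,381 + 348,185 = 561,566, as stated. With 1:1 matching there are at most 2 × 213,381 = 426,762 matched patients.

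**Formula.** For a patient-level exposure that varies within hospitals, with m patients per hospital,

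DEFF = 1 + (m − 1) × ρx × ρy, and SE ratio = √DEFF,

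where ρx and ρy are the between-hospital ICCs of vaccination and of the outcome. With 1:1 arms, an uptake SD of s on the logit gives ρx ≈ 0.25 × s². So s = 0.1 gives 0.0025 and s = 0.2 gives 0.01. On the probability scale these are SDs of about 0.25 × 0.1 = 2.5 and 0.25 × 0.2 = 5 percentage points.

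**Assumed inputs, none in the documents.** 200 to 800 hospitals, s, ρy, event rates and the spread of hospital sizes.

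**Equal-sized hospitals, 426,762 patients.**
- ρx = 0: DEFF = 1.00 for any ρy.
- 800 hospitals (m ≈ 533), ρx = 0.001, ρy = 0.005: SE ratio 1.00.
- 400 hospitals (m ≈ 1,067), ρx = ρy = 0.01: DEFF = 1 + 1,066 × 0.0001 = 1.107, SE ratio 1.05.
- 200 hospitals (m ≈ 2,134), ρx = ρy = 0.05: DEFF = 1 + 2,133 × 0.0025 = 6.33, SE ratio 2.52.

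**Unequal hospitals, continuous outcome, 400,000 patients, no true effect.** Hospital sizes are lognormal with SD 1, and hospital outcome level is independent of uptake. Unequal sizes replace m by about m × e = 2.718m. For 200 hospitals (m = 2,000), s = 0.2 and ρy = 0.05, DEFF ≈ 1 + 2.718 × 2,000 × 0.01 × 0.05 = 3.72, so the SE ratio is 1.93. The table sets this approximation beside simulation.

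| Hospitals | s | ρy | Formula | Simulated SE ratio | Type I error |
|---|---|---|---|---|---|
| 800 | 0.1 | 0.05 | 1.08 | 1.05 to 1.09 | 6% to 7% |
| 200 | 0.2 | 0.05 | 1.93 | 1.83 to 1.87 | 27% to 29% |
| 800 | 0.1 | 0.10 | 1.16 | 1.15 to 1.16 | 8% to 10% |
| 200 | 0.2 | 0.10 | 2.54 | 2.37 to 2.46 | 40% to 43% |
| 200 to 800 | 0 | various | 1.00 | 0.98 to 1.02 | about 5% to 6% |

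Extending ρy down to 0.01 takes the lowest simulated ratio to 1.01. Standard errors clustered on hospital gave error rates of about 4% to 7% throughout.

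**Binary outcomes.**
- 3% event rate, hospital SD 0.5 on the logit, s = 0.1 to 0.2: SE ratio 1.02 to 1.22, type I error 5% to 11%.
- 8% event rate, hospital SD 0.8: SE ratio 1.12 to 2.02, type I error 8% to 31%.
- 400 equal hospitals of 1,067, event rate 3% or 10%, latent ICC 0.01 or 0.05:
  - s = 0: ratio 0.997 to 1.004, coverage 94.7% to 95.2%.
  - s = 0.1 to 0.2: ratio 1.00 to 1.07, coverage 95.3% to 93.2%.
  - s = 0.4: ratio 1.02 to 1.28, coverage 94.5% to 87.3%.

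**The case against.** **A stronger reading that fails.** A reader might infer that correlation within hospitals makes the intervals too narrow in any event. The familiar factor 1 + (m − 1) × ρy would give 1 + 1,066 × 0.01 = 11.7 for 400 hospitals and ρy = 0.01. That factor applies when whole hospitals are exposed or unexposed. Here vaccination is a patient's own exposure before admission, so a hospital can hold both groups and its outcome level cancels from the contrast. With equal uptake everywhere the simulated ratio is 0.98 to 1.02. One exception is a vaccine effect that itself differs between hospitals: with an assumed SD of 0.1 on the log-odds, the ratio was 1.11 and coverage 90.4%.

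**The premise is undocumented.** Neither document says that uptake differs between hospitals, and the range of results runs from negligible to large. This stands, and it is why the point is conditional.

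**Hospitals as fixed.** The programme covers over 99% of the population, so one may hold that its hospitals are not a sample. With hospitals held fixed (ICC 0.05, s = 0.1 to 0.2), the SD of the estimate was 0.99 to 1.02 times the model SE. But the estimate was then shifted by up to 0.88 SE through hospital imbalance, so the interval is still not sound. What stands is that widening the interval does not remove that shift. A within-hospital estimator does: its ratio was 0.99 to 1.03 and its type I error 4.4% to 5.5%.

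**Where the harm falls.** The plan promises CIs only for infections and mortality, while the largest ratios are for continuous outcomes, which get t-tests. This also stands: the 2.5 figure must not be read onto the odds ratios.

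**Conclusion.** The point holds conditionally. As written, the plan neither matches on hospital nor allows for it in its standard errors. If uptake is the same in every hospital and the vaccine effect is common, nothing is lost. If uptake differs between hospitals, the tests reject too often and the intervals under-cover, even without any link between uptake and hospital outcome level.

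Under the assumed inputs the true SE is about 1.0 to 2.5 times the stated SE for continuous outcomes. It is about 1.0 to 1.2 times for rarer outcomes with modest hospital variation, and up to about 2.0 for a binary outcome with strong hospital variation. The documents cannot place the study within these ranges, so they do not support a statement that the reported intervals are in fact wrong. The change is still worth making, because clustered intervals are practically the same as the naive ones when uptake does not vary. The named tests' treatment of matched pairs is a separate matter, not assessed here.

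**What to change.** In section 5, state whether the claims carry an identifier of the treating hospital; the documents mention none. If they do:

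- Compute the CIs and p-values for all outcome comparisons with a variance clustered on treating hospital. This covers infections, mortality, intensive care use, length of stay and expenditure.
- Recast the chi-square and t-test outcome comparisons as regressions, so that the clustered variance can be applied and an interval reported.
- Report a hospital-adjusted (within-hospital) estimate beside each as a check. A within-hospital odds ratio is conditional on hospital, so a small difference from the main odds ratio is expected.
- Report the number of hospitals and the spread of uptake between them, so that readers can judge the size of the problem.

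If there is no identifier, state the limitation. The cost is a little more than a software option, because the simple tests are replaced, and the intervals become somewhat wider where uptake varies. No new patients or data collection are needed if the identifier is already held.

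### Three of the seven primary outcomes (intensive care use, length of stay, expenditure) have no declared effect measure, 95% CI or adjusted model

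*Combined protocol and SAP*

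**What the plan says.** Section 3 (Outcomes) gives a single list of primary outcomes, "assessed within 30 days postadmission, included" pneumonia, septicemia, urinary tract infection, intensive care use, hospital length of stay, total expenditure and mortality. Nothing ranks one above another.

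Section 5 (Statistical Analysis) has three bullets that could bear on them:

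- Categorical variables are "summarized as counts and percentages; compared using the *chi-square test".
- Continuous variables are given as mean ± SD and "compared using *independent t-tests".
- The risk-estimation bullet declares adjusted odds ratios with 95% CIs, which "were derived from logistic regression to assess IV effects on infections and mortality".

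The first two bullets name no outcome, effect measure, interval or adjustment. The third names its scope.

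Confounding is handled for the whole cohort by 1:1 propensity score matching (Sections 2 and 5). The propensity model is described as "including clinically relevant covariates (Table 1") and the matching as greedy, "with a caliper width of 0.2 SD of the logit of the propensity score". Table 1 is cited for the propensity model only. The covariates behind the adjusted odds ratios are not listed.

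**The concern.** The only declared effect measure, interval and outcome model stop at infections and mortality. "Intensive care use", "Hospital length of stay" and total expenditure stand on the same primary footing but receive, at most, a significance test and arm-level summaries. Intensive care use shows the inconsistency most plainly: taken as any versus none, it would fit the same logistic model as mortality.

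Two things are at stake. First, the choice of measure and of adjustment for these three outcomes is not fixed, so it could be made after the results are seen. Second, in a cohort this large a p-value says little about size. The useful result for stay and expenditure is the difference with its interval, and the plan does not commit to one.

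**Working it through.** **The plan's own figure.** The documents give no sample-size, power or alpha figure. The one total that can be checked is the cohort in Section 2: 213,381 + 348,185 = 561,566, which agrees exactly.

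**Outcomes against methods.**

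| Primary outcome (Section 3) | Adjusted OR with 95% CI (Section 5) | Otherwise, the only line that could apply |
|---|---|---|
| Pneumonia | yes | |
| Septicemia | yes | |
| Urinary tract infection | yes | |
| 30-day mortality | yes | |
| Intensive care use | no | chi-square test |
| Length of stay | no | independent t-test |
| Total expenditure | no | independent t-test |

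Four are covered and three are not: 3/7 = 43%. Nothing else in the document fills the gap. Tables S1 and S2 hold infection codes and vaccine types.

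**Why a test alone is not enough here.** The number of matched pairs is not given. If every vaccinated patient were matched (an assumed upper bound) and the arms treated as independent, the 95% half-width for a mean difference is 1.96 × sqrt(2/213,381) = 0.006 SD. That is 0.03 to 0.07 days for an assumed SD of 5 to 12 days. With a quarter of the pairs it is 0.012 SD. Very small differences would be statistically significant.

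**Ignoring the pairing.** With n pairs, outcome SD σ and within-pair correlation ρ, the variance of the mean difference is 2σ²(1−ρ)/n. The unpaired test uses 2σ²/n. The SE ratio is 1/sqrt(1−ρ), equivalent to losing a fraction ρ of the pairs. The documents do not give ρ, so a range is assumed:

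| Assumed ρ | SE ratio | SE overstated by | Pairs effectively lost |
|---|---|---|---|
| 0.05 | 1.026 | 2.6% | 5% |
| 0.10 | 1.054 | 5.4% | 10% |
| 0.20 | 1.118 | 11.8% | 20% |

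**What covariate adjustment would change.** This was simulated with assumed inputs: a vaccinated share of 213,381/561,566 = 38%, five normal covariates, no true effect, and greedy 1:1 matching with the plan's caliper. Matching was without replacement, which the plan does not state.

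- *Continuous outcome* (5 scenarios, 60 datasets of 20,000 patients each; 83% to 99.8% of vaccinated patients matched; within-pair correlation 0.07 to 0.28). The t-test SE divided by the adjusted robust SE was 1.035 to 1.179. Unadjusted minus adjusted estimates were 0.0001, 0.0005, 0.0008, 0.0018 and 0.0034 SD (Monte Carlo SE 0.00004 or less). The largest is 0.0034 × 5 = 0.02 days to 0.0034 × 12 = 0.04 days at the assumed SDs. Robust divided by pair-clustered SE was 0.9997 to 1.0009.
- *Skewed, cost-like (log-normal) outcome* (3 scenarios, 500 datasets of 3,000). The adjusted 95% CI with robust SE covered 94.2%, 96.4% and 96.0%. The Monte Carlo SE is sqrt(0.95 × 0.05/500) = 1.0 percentage point, so all are consistent with 95%. The t-test SE ratio was 1.036 to 1.099, and robust divided by clustered SE was 1.001 to 1.015.
- *Binary outcome at 9% to 11% risk* (3 scenarios, 400 datasets of 3,000). Adjusted logistic coverage was 95.8%, 95.0% and 96.3% (Monte Carlo SE 1.1 points). Ordinary divided by clustered SE was 0.9995 to 1.0003.

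Once covariates are adjusted for, clustering by pair changes the SE by 0.1% or less, or up to 1.5% for the skewed outcome.

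**The case against.** The strongest reply is that nothing is actually broken. The generic bullets, read naturally, do cover the three outcomes. A t-test on means implies a difference in means, and a reader with means, SDs and group sizes can compute the crude difference and an unpaired interval. Matching already addresses confounding for every outcome, and comparing matched groups without further regression is an accepted analysis. The consequences look slight: taking the 0.07-day half-width at an assumed SD of 12 and removing the largest simulated SE excess gives 0.072/1.179 = 0.06 days. The SE figures also rest on correlations, SDs and covariate structures that the documents do not supply.

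Much of this stands. The tests are valid, size is not hidden, bias is small, and the magnitudes are illustrative. The closed-form ratios describe unadjusted comparisons only; the gain from the proposed change is the simulated comparison of the t-test SE with the adjusted SE.

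It does not close the gap. Arm summaries from which a reader can derive an estimate are not a declared estimate. The plan itself asks for adjusted estimates on top of matching for four primary outcomes and gives no reason to treat the other three differently.

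Two further cautions are fair. The documents do not say whether intensive care use is any versus none or a number of days. Table 1 is not in the text available, so its contents cannot be checked here.

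**Conclusion.** The concern holds and should be fixed; it does not undermine the matched design. The count of three in seven comes straight from the text and needs no assumption. The cost in precision does need assumptions: across the simulated settings the unadjusted t-test's SE was 3.5% to 17.9% larger than the adjusted one. Residual imbalance within the caliper shifted the estimate by no more than 0.0034 SD. The main gain from acting is a declared adjusted estimate with its interval, with some precision as a secondary benefit. Removal of bias is not the argument, and neither is any inflation of the type I error rate.

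**What to change.** In the matched cohort:

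1. Define intensive care use as any versus none, if that is what is meant, and add it to the planned adjusted logistic regression, reported as an odds ratio with 95% CI.
2. Report length of stay and total expenditure as covariate-adjusted mean differences (vaccinated minus nonvaccinated) with 95% CIs, from linear regression with robust standard errors. Other models could serve; this one keeps the result in days and in currency.
3. State that the propensity-score covariates in Table 1 are the adjustment set for all seven outcomes.
4. Keep the arm-level summaries. Clustering the robust standard errors by matched pair is optional.

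The cost is a few lines of analysis on data already held and two or three sentences in Section 5. The document is written in the past tense, so if the analyses are already done, the added estimates should be labelled as not prespecified. The change would then improve the reporting but could not restore prespecification.
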